5.3.3.2. Withdrawal from Study Follow-Up

A subject will be withdrawn from the study if the subject meets any of the following reasons. The subject will be informed of their treatment assignment before being withdrawn from the study.

- As deemed necessary by the site principal investigator or appropriate sub-investigator for noncompliance or other reasons.
- Subject withdrawal of consent.
- Subject lost to follow-up.
- Termination of the study.

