3.1.2. Secondary

- To assess the clinical response of early empiric antifungal therapy with fluconazole at Day 22 in subjects with coccidioidomycosis pneumonia regardless of adherence with the study intervention.
- To assess the clinical response of early empiric antifungal therapy with fluconazole at Day 43 in subjects with coccidioidomycosis pneumonia regardless of adherence with the study intervention.
- To compare the clinical response and its individual components over time, by treatment group, in subjects with coccidioidomycosis pneumonia.
- To assess the impact of early empiric antifungal therapy with fluconazole on days lost from work or school and responses to the SF-12v2 and PROMIS Item Bank v2.0 - Ability to Participate in Social Roles and Activities - Short Form 4a in subjects with coccidioidomycosis pneumonia.
- To assess the effect of early empiric antifungal therapy with fluconazole through Day 43 in subjects with coccidioidomycosis pneumonia on all-cause mortality by treatment group.
- To assess whether early empiric antifungal therapy with fluconazole at Day 22 is non-inferior to placebo as defined by clinical response at Day 22 in all randomized subjects, regardless of coccidioidomycosis pneumonia status or adherence with study intervention, with baseline and follow-up FLEET-CAP scores.

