5.3.4. Handling of Withdrawals and Discontinuation of Administration

The primary reason for withdrawal from the study will be recorded on the Study Status data collection form. Subjects will be encouraged to complete the Early Termination Visit. The Early Termination Visit procedures are listed in Section 7.6. Although subjects are free to withdraw at any time or may be withdrawn by the site principal investigator or appropriate sub-investigator at any time, subjects who receive at least one dose of the study drug will be encouraged to remain in the study for follow-up safety assessments and collection of clinical outcome data. Every attempt will be made to follow all serious adverse events ongoing at the time of early withdrawal to resolution.

In the case of subjects who fail to appear for a follow-up safety assessment, extensive effort (i.e., three documented contact attempts via phone calls, e-mails, etc., made on separate occasions and

followed by a certified letter) will be made to locate or recall them, or at least to determine their health status. These efforts will be documented in the subject's records.

See the appropriate section of the Manual of Procedures (MOP) for alternate follow-up requirements.

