11.2. Sample Size Considerations

11.2.1. Sample Size for Per Protocol Analysis Population

The primary analysis will compare the proportion of subjects achieving clinical response at Day 22 among efficacy evaluable subjects, defined as subjects in the Cocci-Positive Per Protocol analysis population who meet the case definition of coccidioidomycosis pneumonia who were compliant with the intervention administration and have coccidioidal serology data available at the Day 1 and 22 visits. We further assume that the clinical response proportion at Day 22 will be 0.20 in the placebo arm, and 0.40 in the fluconazole arm. As described in section 11.2.3, enrollment will continue until 200 subjects are evaluable for efficacy, 100 in each treatment arm, which suffices for 88% power for the Z test with unpooled variance to compare proportion of clinical responses at Day 22 at the two-sided level of 0.05. This is the primary sample size calculation which forms the basis for target enrollment to the study and for subsequent sample size re-estimation procedures at scheduled interim analyses while the study is enrolling.

A secondary analysis in the Cocci Positive Modified Intent-to-Treat population will compare the proportion of responders at Day 22, treating subjects dropping out before the Day 22 visit as non-responders. Assuming that the probability of drop-out before Day 22 is 20% among cocci-positive subjects, we would expect that 250 cocci-positive subjects would be available for this secondary analysis as a result of reaching the target sample size of 200 cocci-positive subjects with Day 22 follow-up for the primary analysis. Since subjects who drop-out are considered non-responders, the probability of response in the control-arm subjects would be $0.8 * 0.2 = 0.16$, and in the treated subjects would be $0.8 * 0.4 = 0.32$. The Z-test with unpooled variance has power of 85% to detect this difference in response proportions with 125 cocci-positive subjects per arm.

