11.4. Final Analysis Plan

11.4.1. Analysis Populations

Safety Analyses:

- Safety population – This safety analysis population includes all subjects who took at least one dose of study medication.

Efficacy Analyses:

- Intent-to-Treat (ITT) population – This efficacy analysis population includes all randomized subjects.
- Cocci Positive Modified Intent-to-Treat (mITT) population – This efficacy analysis population includes all randomized subjects who meet the case definition of coccidioidomycosis pneumonia and took at least one dose of study medication. Note that it is not necessary for a subject to be adherent to study drug to be eligible for inclusion in the mITT population.
- All Randomized Modified Intent-to-Treat (mITT) population – This efficacy analysis population includes all randomized subjects who took at least one dose of study medication regardless of cocci-status. Note that it is not necessary for a subject to be adherent to study drug to be eligible for inclusion in the mITT population.

- Cocci Positive Per-Protocol (PP) population – This efficacy analysis population includes randomized subjects who meet the case definition of coccidioidomycosis pneumonia who were compliant with the intervention administration and have coccidioidal serology data available at the Day 1 and 22 visits.
- All Randomized Per-Protocol (PP) population – This efficacy analysis population includes randomized subjects who were compliant with the intervention administration regardless of cocci-status and have coccidioidal serology data available at the Day 1 and 22 visits.

Adherence is assessed at each study visit depending on the fraction of expected pills taken on or before that time point. If at any visit the subject's cumulative fraction of pills taken drops below 80%, they are deemed non-adherent. This decision is not reversible, even if the subject's cumulative fraction of pills taken rises above 80% at a future visit.

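### Section 5.3.3.2 lets a site end follow-up for undefined noncompliance, against objectives that apply regardless of adherence; the main exposure is the Day 43 analysis (SO 2)

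*Combined protocol and SAP*

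**What the plan says.** The protocol separates two events. Section 5.3.3.1 covers stopping study drug while the subject continues to be followed; inability to keep to the visit schedule is one of its reasons. Section 5.3.3.2 covers leaving the study altogether, and the subject learns the assignment first. Its first ground is "As deemed necessary by the site principal investigator or appropriate sub-investigator for noncompliance or other reasons". The term is not defined there. Elsewhere it has two senses: Section 11.4.1 uses it for falling below 80% of expected pills, and Section 15.6 for any breach of the protocol, GCP or the manual of procedures.

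Other sections point the other way:

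- Section 3.1.2 sets SO 1 and SO 2 "in subjects with coccidioidomycosis pneumonia regardless of adherence with the study intervention". SO 6 covers all randomized subjects, whatever their coccidioidomycosis status or adherence.
- Section 11.4.1 says of both mITT populations that "it is not necessary for a subject to be adherent to study drug". Of the ITT population it says: "This efficacy analysis population includes all randomized subjects".
- Section 5.3.4 says that dosed subjects "will be encouraged to remain in the study for follow-up safety assessments and collection of clinical outcome data", although the same sentence also allows the investigator to withdraw them at any time.

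On missing outcomes, Section 11.2.1 describes the Day 22 analysis in the cocci-positive mITT as "treating subjects dropping out before the Day 22 visit as non-responders". For SO 6 it counts cocci-positive drop-outs before Day 22 as non-responders and cocci-negative ones as responders.

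**The concern.** The primary analysis is per-protocol, restricted to adherent cases. The analyses that ignore adherence are the main check on selection by adherence. They work only if nonadherent subjects are still observed. A clause that lets a site end follow-up because of nonadherence turns outcomes that could have been collected into missing ones. It does so at the investigator's discretion, and for reasons such as poor tolerability or lack of improvement that may differ between arms.

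There is a second cost. Section 5.3.2 keeps the blind until the Day 43 assessments are complete, whereas Section 5.3.3.2 reveals the assignment on withdrawal. Section 7.4.1 then invites such subjects to remain in follow-up. Any later scores, which are mostly self-reported symptoms, would come from someone who knows the assignment.

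**Working it through.** **1. The plan's own figures.** Inputs from Section 11.2.1: response 0.20 and 0.40 in cases, 0.70 in non-cases; 20% drop-out before Day 22; 20% of subjects cocci-positive; non-inferiority margin 0.05; two-sided level 0.05.

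- SO 1, 125 per arm. Rates are 0.8 × 0.20 = 0.16 and 0.8 × 0.40 = 0.32. SE = √[(0.16 × 0.84 + 0.32 × 0.68)/125] = 0.0531. Power = Φ(0.16/0.0531 − 1.96) = 85.4% (stated 85%).
- SO 6, 500 per arm. Rates are 0.640 and 0.672. SE = √[(0.640 × 0.360 + 0.672 × 0.328)/500] = 0.0300. Power = Φ((0.05 + 0.032)/0.0300 − 1.96) = 78.0% (stated 78%). With 625 per arm it is 86.3% (stated 86%).

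Both reproduce.

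**2. What withdrawal for low adherence does to each analysis.**

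- *SO 1 and SO 6 (Day 22).* Section 3.2.1 first assesses adherence on Day 22, and Table 12 has no scheduled visit between Day 1 and Day 22. Section 7.3.1 puts the pill count, the FLEET CAP score and the serology draw in that one visit. Barring an unscheduled contact, the site learns of skipped pills when the Day 22 outcome is collected. If the outcome is missing, it is imputed.
- *SO 2 (Day 43).* Section 3.2.2 lets an earlier response count, so a Day 22 responder loses nothing on this endpoint. A Day 22 non-responder with a low pill count can be withdrawn at that visit and lose the Day 29 and Day 43 scores. The drop-out rules in Section 11.2.1 are written for Day 22. Table 11 says that the SO 1 analysis is repeated at Day 43 with a time-to-event analysis added, but states no rule for a missing Day 43 outcome. The censoring rule in Section 11.4.1 concerns subjects dropped from the per-protocol populations.
- *Cocci-positive mITT membership.* Case criteria 2 to 4 in Section 3.2.1 each need a sample after Day 1. A case withdrawn with neither a Day 22 nor an Early Termination sample can qualify only under criterion 1, on two positive Day 1 tests. Otherwise the subject is not in this population and is not imputed. A case withdrawn at Day 22 also loses the Day 29 draw, but the Day 22 sample still allows every criterion to be met.

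**3. Size.** Of 125 cases per arm, 125 × 0.8 = 100 are expected to have Day 22 follow-up. On the plan's rates, 100 × (1 − 0.20) = 80 placebo and 100 × (1 − 0.40) = 60 fluconazole cases are then non-responders. That is the pool from which SO 2 could lose data. The documents do not give the share with low adherence, nor the share a site would withdraw, so no count follows.

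For Day 22, assume that 5, 10 or 15 points of the 20% drop-out were avoidable withdrawals, now retained and observed (r = 0.05, 0.10, 0.15).

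- If retained cases respond at 0.20 and 0.40, SO 1 power becomes 88.2%, 90.5% or 92.6%, and SO 6 power at N = 1,000 becomes 79.4%, 80.8% or 82.2%.
- If retained cases respond at 0.20 in both arms, the rates are 0.16 + 0.20r and 0.32 + 0.20r and the difference stays 0.16. SO 1 power becomes 84.4%, 83.5% or 82.6%, and SO 6 power 77.4%, 76.9% or 76.5%.

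The change in power is modest, and its sign depends on how nonadherent subjects would respond.

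**The case against.** A reader might infer that the clause removes nonadherent subjects from SO 1, SO 2 and SO 6. The documents do not support that. Population membership does not depend on adherence, SO 6 runs in the ITT population, and Day 22 drop-outs are imputed. The phrase about baseline and follow-up scores in the SO 6 objective could be read as a restriction to observed subjects, but Section 11.2.1 and Table 11 treat SO 6 as an ITT analysis with imputation. Literal removal arises only through missing serum.

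A reader might also infer a fixed loss of effect. If 10% of fluconazole and 5% of placebo cases were withdrawn and imputed, the difference would be 0.40 × 0.90 − 0.20 × 0.95 = 0.170 instead of 0.200. But those rates are in no document, the plan's mITT difference is already 0.16 after drop-out, and noncompliance withdrawals may already lie within the 20%. The sum also assumes that people not taking fluconazole would respond at 0.40. If they responded at 0.20, observing them would give (0.90 × 0.40 + 0.10 × 0.20) − 0.20 = 0.180, a gap of 0.010 rather than 0.030.

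The protocol also has safeguards. The Early Termination Visit (Section 7.4.1) collects FLEET CAP and full serology before Visit 04. Section 6.5 answers missed doses with counseling. Section 11.4.1 envisages nonadherent subjects returning at later visits. Section 11.4.4.1 compares case counts by arm and allows sensitivity analyses for drop-out.

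All of this stands, and it narrows the point. It does not resolve the conflict. Attendance at the Early Termination Visit is only encouraged, and one score at that visit does not replace Day 43. Reading noncompliance as missed visits does not help either, since Section 5.3.3.1 already lists inability to keep to the visit schedule under stopping drug with continued follow-up.

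**Conclusion.** The point holds as a conflict between sections. Section 5.3.3.2 permits a site to end follow-up and unblind for an undefined noncompliance that can include skipped pills, while the objectives, the mITT definitions and Section 5.3.4 call for those subjects to be observed. Exposure at Day 22 is limited. The main exposure is SO 2, for Day 22 non-responders with low adherence. The secondary one is the cocci-positive mITT, for cases with no serum after Day 1. The size cannot be derived, because the 20% drop-out is not split by reason; the ranges above rest on assumed shares. The stated power figures need no correction. The conclusion rests on the text as written: Section 11.4.4 defers analysis details to a separate statistical analysis plan, which could supply a Day 43 rule but could not recover scores never collected.

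**What to change.** In Section 5.3.3.2, remove noncompliance with study drug as a ground for withdrawal from follow-up. State that it alone neither ends follow-up nor triggers unblinding, and that such subjects keep the scheduled Day 22, 29 and 43 FLEET CAP scores, serology and mortality ascertainment. Keep investigator discretion for other reasons, but require the reason to be stated; removing all discretion would go further than the problem requires. Align Section 5.3.4 and the Study Status form. Because some drop-out will remain, add a missing-data rule for Day 43.

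The cost is a short protocol edit and a memo to sites. The downside is that sites must keep following poorly adherent subjects, at visits already scheduled.

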5.3.4. Handling of Withdrawals and Discontinuation of Administration

The primary reason for withdrawal from the study will be recorded on the Study Status data collection form. Subjects will be encouraged to complete the Early Termination Visit. The Early Termination Visit procedures are listed in Section 7.6. Although subjects are free to withdraw at any time or may be withdrawn by the site principal investigator or appropriate sub-investigator at any time, subjects who receive at least one dose of the study drug will be encouraged to remain in the study for follow-up safety assessments and collection of clinical outcome data. Every attempt will be made to follow all serious adverse events ongoing at the time of early withdrawal to resolution.

In the case of subjects who fail to appear for a follow-up safety assessment, extensive effort (i.e., three documented contact attempts via phone calls, e-mails, etc., made on separate occasions and

followed by a certified letter) will be made to locate or recall them, or at least to determine their health status. These efforts will be documented in the subject's records.

See the appropriate section of the Manual of Procedures (MOP) for alternate follow-up requirements.

5.3.5. Subject Replacement

Subjects who withdraw consent, are withdrawn or terminated from the study, or are lost to follow-up after signing the informed consent form, randomization, and after ingesting study drug will not be replaced. Those subjects who withdraw or are terminated from the study before ingestion of the study drug will be replaced.

5.3.6. Termination of Study

Although the study Sponsor has every intention of completing the study, it reserves the right to terminate the study at any time for clinical or administrative reasons. Reasons for termination include, but are not limited to, study closure due to DSMB review and recommendation; and/or at the discretion of DMID.

6. STUDY INTERVENTION/INVESTIGATIONAL PRODUCT

6.1. Study Product Description

Fluconazole is the first of a new subclass of synthetic triazole antifungal agents. It is designated chemically as 2,4-difluoro-alpha, alpha1,1-bis(1H-1,2,4-triazol-1-ylmethyl) benzyl alcohol with an empirical formula of C₁₃H₁₂F₂N₆O and molecular weight of 306.3.

6.1.1. Acquisition

Fluconazole Capsules

AAIPharma Services Inc. will perform the encapsulation, packaging and labeling of study drug according to applicable regulatory requirements. Fluconazole will be acquired through the DMID Clinical Agents Repository (CAR, Fisher BioServices).

Fluconazole will be shipped from the DMID CAR to the study site upon request and approval by DMID.

Placebo Capsules

AAIPharma Services Inc. will perform the encapsulation, packaging and labeling of study drug according to applicable regulatory requirements. Placebo will be acquired through the DMID Clinical Agents Repository (CAR, Fisher BioServices).

Placebo will be shipped from the DMID CAR to the study site upon request and approval by DMID.

6.1.2. Formulation, Packaging, and Labeling

Fluconazole Capsules

Fluconazole will be supplied as 200mg over encapsulated tablets. Each gelatin capsule will contain two-100mg fluconazole tablets and microcrystalline cellulose for overfill. All study product will be packaged in identical containers each containing 34 capsules. Each container will also be labeled in compliance with applicable regulatory requirements, including the FDA-required cautionary statement “Caution- New drug -Limited by Federal (or United States) Law to Investigational Use Only.”

Placebo Capsules

Placebo will be supplied as matching gelatin capsules containing microcrystalline cellulose only. In order to maintain the blind, the gelatin capsules are the same size, weight, and color as the capsules containing fluconazole tablets. All study product will be packaged in identical containers each containing 34 capsules. Each container will also be labeled in compliance with

applicable regulatory requirements, including the FDA-required cautionary statement “Caution- New drug -Limited by Federal (or United States) Law to Investigational Use Only.”

6.1.3. Product Storage and Stability

Fluconazole

Fluconazole capsules must be stored at 20°C to 25°C (68°F to 77°F) [See USP Controlled Room Temperature].

Placebo

Placebo capsules must be stored at 20°C to 25°C (68°F to 77°F) [See USP Controlled Room Temperature].

6.2. Dosage, Preparation and Administration of Study Intervention/Investigational Product

Fluconazole

Fluconazole 400 mg (administered orally as two 200mg capsules) once daily for a minimum of 42 days.

Pills should be maintained as dispensed and not scored, cut, crushed, or otherwise divided for ease of swallowing. The capsules will be administered with water sufficient for the subject to swallow the required number of capsules.

Placebo

Placebo (administered orally as two matching placebo capsules) once daily for a minimum of 42 days.

Pills should be maintained as dispensed and not scored, cut, crushed, or otherwise divided for ease of swallowing. The capsules will be administered with water sufficient for the subject to swallow the required number of capsules.

6.3. Modification of Study Intervention/Investigational Product for a Subject

No modifications of study product are planned at this time. If a subject experiences an allergic reaction to the study drug, they will be taken off of the study drug.

6.4. Accountability Procedures for the Study Intervention/Investigational Product(s)

After receipt of the study product, the site principal investigator (PI) is responsible for distribution and disposition of these study products, and has ultimate responsibility for drug

accountability. The site PI may delegate this responsibility to the site pharmacist. Study product records must be maintained and document logs of receipt, accountability, and storage temperature conditions. These study product accountability and dispensing logs must be maintained in the study file. Upon completion of the study and after the final monitoring visit, unused study product will be retained until monitored and released for disposition as per the Sponsor. For hospitalized subjects, study product will be handled, stored and administered according to procedures outlined in the protocol-specific MOP as appropriate. See above for specific storage conditions for the study product.

6.5. Assessment of Subject Compliance with Study Intervention/Investigational Product/Investigational Device

The investigator will maintain records documenting all study product administered to each subject for the entire study period. For hospitalized subjects, procedures for documentation of study product administration are outlined in the protocol-specific MOP as appropriate. Subjects will be asked to bring their study product containers to each study visit and will be interviewed regarding medication adherence. The study staff will document any missed doses of study medication by counting any pills remaining in the subjects' containers brought to the visit and provide counseling per study sites' routine procedures to promote adherence to study medication. If the subjects' study product containers are lost or unavailable, subject interview will be used to determine study medication adherence. The study staff will record how study drug adherence information was obtained.

6.6. Concomitant Medications/Treatments

Administration of any medications, therapies, or vaccines will be recorded on the appropriate data collection form. Concomitant medications will include all current medications and medications taken within 30 days prior to signing the informed consent form through Day 43 for all subjects. Prescription and over-the-counter drugs will be included as well as vitamins and supplements.

Use of new medication should prompt evaluation for the presence of a new diagnosis of chronic medical disease or condition.

Any other systemic antifungal not provided as part of the study intervention is prohibited during the treatment period of this study, and prohibited within the 4 weeks prior to enrollment (with the exception of a single dose of fluconazole) as specified in Exclusion Criterion 6.

Medications that might interfere with the evaluation of the investigational product should not be used unless absolutely necessary. Fluconazole is a potent CYP2C9 inhibitor and a moderate CYP3A4 inhibitor. Subjects treated with fluconazole who are concomitantly treated with drugs with a narrow therapeutic window metabolized through CYP2C9 and CYP3A4 should be

considered for additional monitoring of blood levels, lack of efficacy, or increased toxicity of these medications.

The following lists are derived from the FDA package insert and from the information in Up to Date®. It is not a complete list of potential drug-drug interactions, but are lists of agents that are likely to be seen in an ambulatory population.

Antibacterial medications that are prescribed by the health care provider for the treatment of community acquired pneumonia are also not included on this list but are discussed in Section 2.3.1.

Medications in this category include, but are not limited to the following:

